Trial Design	
 
• Controlled, open label, non-randomized, investigation in twelve (12) participants.
 
• Two sites: (1) Miami Veterans Affairs Medical Center; (2) University of Miami Miller School of Medicine.
 
• Informed Consent will be obtained prior to enrollment in the study.
 

Approximate Duration of Patient Participation	
 
• 52 weeks (±7 days) for each subject from Initial Visit until Final Visit.
 
• After implantation of the DBS device on the 8th week, scheduled safety and efficacy assessments will be performed at intervals of 4 weeks until study week 24, and at intervals of 8 weeks thereafter.
 

Approximate Duration of Study	

• End of Study is Defined as Last Subject’s Final Visit

• Total period of study is 36 months, from when 1st subject enrolled.

Study Objective(s)	
Primary: to determine whether Deep Brain Stimulation (DBS) applied bilaterally or unilaterally in the midbrain periaqueductal-periventricular gray (PAG/PVG) region provides acute or long-term relief of chronic SCI associated pain and autonomic dysreflexia.
 
Secondary: to assess the clinical effects of DBS on autonomic functioning; to determine with Aactiva PC+S whether local field potentials in the PAG/PVG can be used to predict the efficacy of DBS in this region

Diagnosis and Main Criteria for Inclusion	Major Inclusion Criteria:		
	Inclusion Criteria	Measure	Rationale
	Age $\geq$ 22	Years of age	Higher rates of neurological recovery if younger.
	Age $\leq$ 60	Years of age	Different injury patterns and higher risk of complications if older
	Level of injury at or above T12	Neurological exam	Eliminates injuries below thoracic level T12, which have different pain pattern
	1. Neuropathic pain at or below the level of injury, as determined based on pain in an area with neurological deficit and described as burning, shooting, electric, stinging etc.		
	2. The injury must have occurred at least 1 year prior to entering the study and participants must have experienced chronic pain for a minimum of six months.		
	3. The disability must have a grade of on the American Spinal Injury Association Impairment Scale (AIS) of ASIA-A, ASIA-B, ASIA-C or ASIA-D as determined by a qualified examiner.		

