
Concomitant Medication
	
Concomitant medications and treatments or procedures pertinent to the study treatment or to any adverse events will be recorded including:
 
 
1) name of drug, treatment, or description of procedure,
 
2) start and end dates and times, and
 
3) clinical indication and/or findings.
 
 
Investigational drugs and any other intervention (not part of the guidelines for management of SCI) known to have a potential impact on outcome will be prohibited.
 
Participants will be allowed to utilize over-the-counter drugs such as NSAIDs, acetaminophen and aspirin. Their use will be documented in the weekly pain assessments. A list of “allowed” medications will be provided to study participants. After the surgery, patients will be allowed to stay on the protocol if they take Tramadol (50-100 mg, 2 times a day for up to 2 weeks) as a rescue drug in addition to their stable medication.
 
The patient must be taking pain medication to maintain a stable level of medication from 4 weeks before surgery to 12 weeks after (the primary endpoint), except on the day of surgery. On the day of the surgery, in the presence of a physician who can provide immediate backup pain control if needed, medications will be stopped until the acute effects of DBS on analgesia have been evaluated.
 
On week 20 during a patient visit under medical supervision, patients will be instructed to take one fewer tablet or a smaller dose tablet, wait 4 hours and then see if their pain becomes worse. If it does become worse, they may take medication to reach the original dose. Subsequently, they may follow this procedure at home or during the following visits.

Study Intervention (Device Usage Protocol)
	

Device
	
The study will use PMA authorized, Class III, implantable, Neurostimulation Systems for Deep Brain Stimulation. The Medtronic Activa PC and PC+S DBS device systems will be used as designed without any modifications.

Study Intervention (Device Usage Protocol)	

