Primary Safety Analysis	
The analyses for safety will focus on changes in reported pain intensity during routine patient visits. All AEs and SAEs will be listed and their incidence compared to historical controls. The primary endpoint analyses will occur at 44 weeks post-implantation.

Secondary Outcomes and Analyses	
The secondary hypothesis concerns autonomic assessment that will also take place during routine patient visits. Heart rate, blood pressure, sweating, body temperature and breathing will also be classified as normal, abnormal, unknown or not obtainable. Lower urinary tract, bowel and sexual function will also be scored.
 
Comprehensive testing sessions will analyze vagal and sympathetic influences on the cardiovascular system, measuring blood pressure and heart rate variability (power spectrum analysis) during sit-up or tilt-table challenge.
 
Assessment of motor and non-pain somatosensory function will be done during visits every 4 weeks. Clinical sensory testing will include Light Touch and Pin Prick tests defined in the ASIA standards [1]. The Beck Depression Inventory (BDI-1a) will also be used, to assess emotional function in neuropathic pain [4]. If BDI assessment (>30) suggests suicidal thoughts, the Columbia Suicide Severity Rating Scale will be used in consultation with a clinical psychologist.

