### 13.3 Inclusion Criteria

- a) Age: 22 - 60 years old at last birthday;
- b) Diagnosis of traumatic SCI at or above the 12th thoracic segment (T12) that occurred >365 days;
- c) Neuropathic pain below the level of injury, as determined based on pain in an area with neurological deficit and described as burning, shooting, electric, stinging etc.

- d) The injury must have occurred at least 1 year prior to entering the study and participants must have experienced chronic pain for a minimum of six months.
- e) The disability must have a grade on the American Spinal Injury Association Impairment Scale (AIS) of ASIA-A, ASIA-B, ASIA-C or ASIA-D as determined by qualified examiners.
- f) Pain (neuropathic) of moderate severity or greater is present, when the patient is taking their routine pain medication, with a score of at least 4 on a numerical rating scale (range of 0 to 10).
- g) Participants who are on medications for other conditions, such as diabetes, will be considered as candidates for this study. The dose will be monitored throughout the trial. (They will be excluded if the drug is being used to treat epilepsy, Parkinson's diseases, or other brain degenerative diseases.)
- h) Participants will be allowed to utilize over-the-counter drugs such as NSAIDs, acetaminophen and aspirin. Their use will be documented in the weekly pain assessments. A list of "allowed" medications will be provided to study participants. After the surgery, patients will be allowed to take stay on the protocol if they take Tramadol (50-100 mg, 2 times a day for up to 2 weeks) as a rescue drug in addition to their stable medication.
- i) The patient must be taking pain medication to maintain a stable level of medication from 4 weeks before surgery to 12 weeks after (the primary endpoint), except on the day of surgery. On the day of the surgery, in the presence of a physician who can provide immediate backup pain control if needed, medications will be stopped until the acute effects of DBS on analgesia have been evaluated.
- j) The participant must be willing to comply with the protocol including all scheduled visits.
- k) Autonomic dysreflexia can be present but is not a necessary requirement. Autonomic dysreflexia will be defined as rise of systolic pressure by more than 30 mm Hg during noxious skin stimulation or when the bladder or bowel are full, or apparently spontaneously over a period of minutes
- l) Literate at 8th grade level or above.

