#### 14.5 Post Implantation Procedures & Follow-up

Procedures performed to evaluate the safety of the investigational procedures and to evaluate subject outcome for this study include:

- A. Beginning one week after surgery, participants will undergo follow-up assessments post-implantation:
  - i. Pain assessments every 2 weeks (ISCI basic pain data set, NPSI), starting on week 10, will assess for development of, or changes in neuropathic pain; more comprehensive pain testing (MPI quantitative sensory testing/allodynia) will take place on comprehensive testing visit weeks (20-week, 32-week, and 52-week).
  - ii. Autonomic Standards Assessment: on on-site visit weeks (BP, HR, sympathetic skin response) and on week 20, week 32, and week 52 (Tilt table response exam). Patient Self-assessment of Autonomic Responses occurs weekly starting on week 3, except on on-site visit weeks.
  - iii. QoL assessments: on on-site visit weeks, starting on week 12 (Beck Depression Inventory (BDI-1a)) and weekly, starting on week 9 (Guy/Farrar Patient Global Impression of Change (PGIC));
  - iv. ASIA motor and sensory assessments: on weeks 20, 32 and 52 to assess any improvement or deterioration in neurological function;
  - v. a qualitative exit interview with audio recording at 52 weeks, giving subject and investigators will be given the opportunity for open comments and questions concerning elements of the study.

- B. Follow-up assessments will take place either at the Miami VA Hospital or at The Miami Project to Cure Paralysis, Department of Neurological Surgery, for regular follow-up visits for 44 weeks post-surgery. At each visit, information will be collected regarding the safety of the treatment, the presence or absence of adverse side effects, and the efficacy of the therapy with respect to recovery of neurological functioning or the development of adverse effects.

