## 17 STATISTICAL CONSIDERATIONS

### 17.1 Safety Analyses:

The analyses for safety will be mainly descriptive, focusing on trends for within-subject differences and changes in reported pain intensity during routine patient visits for the duration of the study. The expected outcome is stable, long-lasting change in the Pain Assessment Scale score from baseline to 44 weeks post-implant .All AEs and SAEs will be listed and their incidence compared to historical controls. The primary safety analysis will be conducted on all patient data when all 12 participants have completed the study.

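### The primary pain time is given as both 12 and 44 weeks after implantation, drug reduction begins at the earlier one, and no specified analysis uses the medication diary

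*Combined protocol and SAP*

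**What the plan says.** Two times are called primary.

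- **12 weeks.** Section 13.3 (i) requires the patient to "maintain a stable level of medication from 4 weeks before surgery to 12 weeks after (the primary endpoint"; the parenthesis labels the 12-week point. The Synopsis row on concomitant medication says the same.
- **44 weeks.** The Synopsis row on the primary safety analysis says "The primary endpoint analyses will occur at 44 weeks post-implantation". The same row says "The analyses for safety will focus on changes in reported pain intensity during routine patient visits". Section 17.1 expects a lasting "change in the Pain Assessment Scale score from baseline to 44 weeks post-implant".

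Both count from an operation placed in study week 8: the Synopsis has "After implantation of the DBS device on the 8th week", and section 14.5 B provides "for regular follow-up visits for 44 weeks post-surgery" within a 52-week study.

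On drug reduction, the Synopsis says: "On week 20 during a patient visit under medical supervision, patients will be instructed to take one fewer tablet or a smaller dose tablet". If pain worsens, the patient may return to the original dose. It adds: "Subsequently, they may follow this procedure at home or during the following visits". The tapering row of Table 2 is marked in the columns for weeks 20 and 32 and for weeks 24, 40 and 48.

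Medication is recorded throughout: Table 2 schedules the diary 50 times, and section 14.6 A requires all medication to be recorded. Section 16 lists no medication outcome. The covariates in section 17.1 are level and completeness of injury and electrode configuration. Sections 12.5, 17.2 and 17.4 give no rule for pain scores obtained after a drug change.

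**The concern.** The two candidate times differ in more than length of follow-up. At 12 weeks, patients should still be on stable background analgesia. At 44 weeks they have had 32 weeks in which to reduce it. A pain change at week 52 that is not read beside drug use therefore combines the effect of stimulation with the effect of altered medication. A patient whose pain is unchanged on fewer drugs would be scored as having no benefit. A patient whose drug use rose after the stable period would look better than stimulation alone made them.

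With 12 unblinded subjects and two labelled primary times, the headline time could also be chosen after the data are seen. The Synopsis says the trial is meant to judge whether a larger study is warranted, so the choice matters.

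**Working it through.** **Inputs.** Implantation in week 8 (Synopsis, duration of participation); lead placement in week 7 (Table 1); primary times of 12 and 44 weeks (above); end of the main study at week 52 (section 12.6.1); assessment weeks from Table 2.

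**1. Reproduce the plan's own figure.** 52 − 8 = 44, so 44 weeks post-implantation is week 52, the final visit.

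**2. Place both primary times on the study calendar.**
- 8 + 12 = week 20, the week in which dose reduction starts.
- 8 + 44 = week 52.
- Gap: 52 − 20 = 32 weeks, which is 32/44 = 73% of post-implant follow-up.
- Counting from lead placement in week 7 gives weeks 19 and 51. The gap is unchanged.

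**3. Stable-medication window.** 8 − 4 = week 4, to 8 + 12 = week 20.

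**4. Pain assessments (ISCI/NPSI row of Table 2).**
- Before surgery: weeks 2, 4 and 6 = 3.
- After implantation: even weeks 10 to 52 = (52 − 10)/2 + 1 = 22.
- Total: 3 + 22 = 25, which matches the count printed in the table.
- Weeks 10 to 20: 6. Weeks 22 to 52: 16. Share after the window: 16/22 = 73%.

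**5. On-site visits after implantation.** Weeks 12, 16, 20, 24, 32, 40, 48 and 52 = 8, of which 5 fall after week 20.

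**6. Tapering visits.** Weeks 20 and 32 (2) plus weeks 24, 40 and 48 (3) = 5, all before week 52. The week-20 rating follows none of them, provided it is taken before that day's dose test. Note 1 to Table 2 places assessments before DBS adjustment but says nothing about their order relative to the dose test.

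**7. Baseline.** Table 1 and section 14.3.1 put baseline at week 2, which is 4 − 2 = 2 weeks before the window opens. If surgery is taken as week 7, the window opens at 7 − 4 = week 3 and the gap is 1 week.

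Items 4 to 6 are shares of the schedule, not of affected data, because reduction after week 20 is optional. The documents give no size for the effect of a drug change on the pain score, and none is assumed here.

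**The case against.** The best reply is that the 44-week sentence sits under safety and only says when analyses are run, so the 12-week label could still define the endpoint. That would hold if the sentence stood alone. But the same row names pain intensity as its focus, section 17.1 measures the pain change to 44 weeks, and the models there take the NRS pain score as their main outcome. Both times concern pain.

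It is also fair to say that little formal inference depends on the choice. Section 17.3 proposes description only, no sample size or success criterion is tied to either time, and section 17.2 follows efficacy from baseline through week 52, so both times will be visible. This limits the severity. It does not say which time is primary, and section 17.1 still lists hypotheses to be tested.

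Four smaller points stand in part.
- The bias need not run one way: over-the-counter drugs and post-surgical rescue medication are allowed even inside the stable period, and drug use could rise later.
- The baseline point is soft. With visits allowed ±7 days, a nominal week-2 assessment may fall inside the window if surgery is counted from week 7.
- The tapering row has no printed count to check against, and some neighbouring rows of Table 2 look displaced. Its start at week 20 does agree with the Synopsis.
- The stimulator-off checks in section 12.5 compare on with off at one visit's medication level. They are useful, but they do not answer the question in Aim 4 (section 11.1) about cumulative change.

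**Conclusion.** The concern holds. The plan gives two primary pain times 32 weeks apart and reconciles them nowhere. The later one comes after up to five scheduled tapering visits, and the medication record has no specified use in the analysis. After the stable-medication period come 16 of 22 post-implant pain assessments (73%) and 5 of 8 on-site visits.

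This is a problem of interpretation, not of error rate or power, and it should be fixed. The calendar rests on implantation in week 8. The figure of five visits rests on the tapering row of Table 2 as it reads. The size and net direction of any shift at week 52 are unknown, and a single-arm, unblinded design limits attribution at either time.

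**What to change.** - **Name one primary pain time.** Reconcile the Synopsis medication row and section 13.3 (i) with the Synopsis primary safety row and section 17.1, and fix the choice before the data are seen.
- **Show pain beside drug use.** Report the NRS change at study weeks 20 and 52. Beside each, list every subject's change in analgesic use from the existing diary, relative to that subject's own pre-surgery use (12 rows). Include over-the-counter and rescue drugs.
- **Fix the order at week 20.** Extend note 1 to Table 2 so that the pain rating precedes the dose-reduction test as well as DBS adjustment.
- **Optional.** Show the already scheduled week-4 and week-6 scores as a sensitivity baseline, noting that they are collected by telephone.

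The cost is some wording, one listing shown at two times and a set order of steps at one visit. The diary and all pain scores are already scheduled, and the medication schedule is left as it is. The drawback is a less simple headline, because pain must be read together with drug use.

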	Active major medical or psychiatric illness (MMSE<25)	History	Vulnerable population
	Significant post-traumatic encephalopathy from head trauma sustained at SCI	History	Vulnerable population
	Languages without local expertise	Family history	Lack of personnel or appropriate outcomes scales
	Pain is only nociceptive, due to muscle spasm	Physical examination	Neuropathic pain is therapeutic target
		
Major Exclusion Criteria: Treatment/Intervention procedure:
 
 
1. Coagulopathy requiring anticoagulation therapy
 
2. Thrombocytopenia or platelet dysfunction
 
3. Peripheral vascular disease
 
4. Comorbid neurological diseases or disorders, including a history of seizures
 
5. Active systemic infection or concurrent immunosuppressive therapy
 
6. Existing implantable cardiac pacemaker, defibrillator or neurostimulator
 
7. Requiring short-wave or microwave diathermy treatment during the course of the study.
 
8. Inability to cooperate
 
9. Any contraindication to MRI studies (All future MRIs, with the exception of brain MRIs, are excluded.)
 
10. Adverse reaction to stimulation (such as inability to stimulate at analgesic levels without causing clinical hypertension or hypotension) or allergy or hypersensitivity to any materials of the neurostimulation system
 
11. Depression, as defined by a Beck Depression Inventory (BDI-1a) score of 30 or above.
 
12. Subjects with any clinically significant abnormality, not expected on the basis of age (age-related), that is seen in magnetic resonance imaging (MRI).
 
	

Approximate Number of Patients
	
A maximum of 12 participants with incomplete or complete SCI and neuropathic pain at or below the level of injury.

Approximate Number of Study Centers
	
Two sites (VA Medical Center & University of Miami - Miller School of Medicine)

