#### Aims:

1. To evaluate any changes in pain relief in the 2nd and 3rd year of deep brain stimulation (DBS) in the midbrain periaqueductal/periventricular gray (PAG/PVG).
2. To assess needs for changes in stimulation parameters (contact selection, voltage, frequency, pulse width) to continue optimal relief.
3. To determine changes in injury status revealed by the ASIA score.
4. To uncover later-occurring adverse effects.

Enrollment. Subjects will preferably continue without a gap at the end of the original 52 week study. However, they may be enrolled at any time during the extension to accommodate the time needed to obtain regulatory approval for the extension or subjects who wish to take a break. An additional informed consent form will be used for enrollment.

Procedures. Subjects will receive continuous DBS in the PAG/PVG from the previously implanted system. They will return every 12 weeks to the study site to optimize the stimulation parameters for pain control. The optimum may drift or may not have been determined previously from the very large range of possible settings. Subjects will leave the visits with a blinded choice of settings (2 to 4, labeled A, B, C D), which they can explore at home. Preliminary findings suggest that pain changes over several days when settings are changed, and that slow recursive testing is the best way to find the optimum. Subjects may request visits

at other times for stimulation adjustment or other study related issues. Some later subjects may have a PC+S generator device implanted, which allows recording from the stimulating leads. Subjects with this device will also undergo brief recording sessions during visits, following the protocol of the first year.

Tests and questionnaires. The study extension will use only questionnaires and study forms from the original study. It will omit autonomic system testing and quantitative sensory testing. On-site assessment will be done in clinical exam rooms and offices of the Miami Project to Cure Paralysis of the University of Miami Miller School of Medicine, including ASIA assessment. If the stimulator settings are producing consistent adequate pain relief, visits may be omitted at the subject's discretion, except for weeks 104 and 156, and assessments will be made by telephone questionnaire.

The following will be assessed every 12 weeks.

- International Spinal Cord Injury pain basic data set (ISCI)
- Neuropathic Pain Symptom Inventory (NPSI)

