- Beck depression inventory (BDI)
- Guy-Farrar patient global impression of change (PGIC)
- Medication usage

In addition, subjects will be asked to keep a pain diary with a morning and evening pain score rated from 0 (no pain) to 10 (worst ever pain). The pain diary will be retrieved at the visits or by telephone.

At weeks 104 and 156, we will determine the ASIA score (American Spinal Injury Association neurological examination, sensory and motor). On week 156, an open ended qualitative exit interview will be conducted with audiovisual recording, including questions on the overall experience, effects on daily life, etc.

Adverse events (AEs) will be recorded immediately after telephone contact by the subject (subject-reported AEs) and during visits to the study site (clinician-reported AEs).

• **Table 1: List of Procedures for planned study**

Screening:	
1	Urine pregnancy test
2	HIV, HBV, HCV testing
3	Laboratory tests (CBC, CMP, BSCP, prothrombin time test)
4	Medical history, Brief neurological and medical examination
5	Autonomic dysreflexia assessment
6	Spinal Cord Injury history
7	ASIA motor / sensory scores
8	Functional and pain assessments
9	Psychological Assessment (MMSE, BDI)
10	Drug abuse screening test
Baseline Procedures (at 2- weeks):	
1	Autonomic dysreflexia assessment
2	Functional and pain assessments
3	Psychological Assessment (MMSE, BDI)
4	ASIA motor / sensory scores
5	Medical history, Brief neurological and medical examination
6	Patient diary on medications
DBS Device Implantation Surgical Procedure:	
1	Initial MRI / CT scan of the spine
2	Chest X-ray; Electro-cardiogram
3	1-Targeting & Lead placement: at 7-week
3	2-DBS & Lead connection: at 8-week
ICU Monitoring/Medical Treatment:	
1	Blood Pressure Monitoring
2	Oxygenation
3	Additional physiological monitoring specific to subject (displayed on telemetry monitor)
4	Laboratory tests (CBC, CMP, BSCP, prothrombin time test)
5	Post op medications (antibiotics, DVT prophylaxis, etc.)
Follow-Up Procedures:	
1	Long-term DBS in PAG/PVG starting on week 8
2	Telephone interview: weekly, except on-site visit weeks, from week 3
3	Pain assessments: on even weeks, starting on week 10
4	Autonomic Standards Assessments: on on-site visit weeks
5	Tilt table response exam: at 20-week, 32-week, and 52-week
6	Beck Depression Inventory: on visit weeks
7	Folstein Mini-Mental State exam: at 20-week, 32-week, and 52-week

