**Additional Surgical Exclusion Criteria:**

- 1) Coagulopathy
- 2) Thrombocytopenia or platelet dysfunction
- 3) Inability to cooperate
- 4) Any clinically significant abnormality, not expected on the basis of age (age-related), that is seen in magnetic resonance imaging (MRI).
- 5) Peripheral vascular disease.
- 6) Depression, as defined by a Beck Depression Inventory (BDI-1a), score 30 or above.
- 7) Existing implantable cardiac pacemaker, defibrillator or neurostimulator.
- 8) Diathermy treatment during the course of the study (unless limited to brain and cervical spine and using a head send-receive coil
- 9) Adverse reaction to stimulation (such as inability to stimulate at analgesic levels without causing clinical hypertension or hypotension) or allergy or hypersensitivity to any materials of the neurostimulation system
- 10) Comorbid neurological diseases or disorders, including a history of seizures

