specified: for heart rate, bradycardia, tachycardia or other dysrhythmias; for blood pressure, systolic blood pressure under 90 mm Hg, orthostatic hypotension, autonomic dysreflexia; for sweating, hyperhidrosis above lesion, hyperhidrosis below lesion, hyperhidrosis below lesion; for body temperature, hyperthermia, hypothermia; for breathing, requiring full ventilatory support, requiring partial ventilatory support, impaired not requiring ventilatory support. Lower urinary tract, bowel and sexual function will be scored on the following: awareness of need to empty bladder and ability to prevent urine leakage; sensation of need for bowel movement, ability to prevent stool leakage, voluntary anal sphincter contraction; genital arousal (psychogenic and reflex), orgasm, ejaculation (male), and sensation of menses (female).

Comprehensive testing sessions will analyze vagal and sympathetic influences on the cardiovascular system, measuring blood pressure and heart rate variability (power spectrum analysis) during sit-up or tilt-table challenge. However, if a subject is not able to tolerate the tilt table response exam to completion, he/she will not be required to fulfill this test at subsequent visits. The neurologist will decide whether it is recommended for subjects to undergo this assessment thereafter. Additionally, the test will not be required for subjects not expected to show autonomic dysreflexia because of their lower level of injury, as determined by the neurologist.

Assessment of motor and non-pain somatosensory function will be done during visits every 4 weeks. Clinical sensory testing will include Light Touch and Pin Prick tests defined in the ASIA standards [1]. The Beck Depression Inventory (BDI-1a) will also be used, to assess emotional function in neuropathic pain [4]. A score of 30 or above indicates severe depression. If BDI assessment suggests suicidal thoughts, the Columbia Suicide Severity Rating Scale will be used in consultation with a clinical psychologist.

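### The synopsis attaches a BDI score above 30 to the trigger for the Columbia suicide scale, while section 15 gives the same trigger with no score; the score should be deleted

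*Combined protocol and SAP*

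**What the plan says.** The Columbia Suicide Severity Rating Scale is named in two places only.

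- **Section 3, Synopsis, Secondary Outcomes and Analyses:** "If BDI assessment (>30) suggests suicidal thoughts, the Columbia Suicide Severity Rating Scale will be used", in consultation with a clinical psychologist.
- **Section 15, Safety:** "A score of 30 or above indicates severe depression. If BDI assessment suggests suicidal thoughts", followed by the same instruction. The first sentence classifies severity. The second triggers the scale and contains no score.

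The BDI cut-off appears in two further places, both as a surgical exclusion:

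- **Synopsis, treatment/intervention exclusions:** "Depression, as defined by a Beck Depression Inventory (BDI-1a) score of 30 or above".
- **Section 13.4, additional surgical exclusions:** "Depression, as defined by a Beck Depression Inventory (BDI-1a), score 30 or above".

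Section 12.6.1 (extension) repeats the BDI. Its list is introduced by "The following will be assessed every 12 weeks" and includes "Beck depression inventory (BDI". It adds that "The study extension will use only questionnaires and study forms from the original study", and it gives no suicidality trigger of its own. It also says "If the stimulator settings are producing consistent adequate pain relief, visits may be omitted" at the participant's discretion, except at weeks 104 and 156, with assessment by telephone instead.

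**The concern.** This instruction directs a clinical safety action in people with drug-refractory chronic pain and a brain implant, so it should read the same wherever it appears. The synopsis merges two things that section 15 keeps apart: how depressed the participant is overall, and whether the answers suggest suicidal thoughts. A participant can give a worrying answer while the total stays moderate. Under section 15 that participant goes to the Columbia scale; under a literal reading of the synopsis the participant does not. The protocol does not say whether the synopsis or the body governs. The extension relies on the original study's forms, so it inherits the ambiguity.

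**Working it through.** No power, error-rate or sample-size figure is involved. The check compares the texts and then counts the forms to which the rule applies.

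**1. The two triggers side by side.** Assume whole-number BDI totals, so that above 30 means 31 or more.

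| Answers suggest suicidal thoughts | BDI total | Synopsis, read literally | Section 15 |
|---|---|---|---|
| Yes | 31 or more | Use the scale | Use the scale |
| Yes | exactly 30 | Not triggered | Use the scale |
| Yes | below 30 | Not triggered | Use the scale |
| No | any | Not triggered | Not triggered |

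The texts disagree in the second and third rows. Apart from the parenthesis, the two sentences are identical.

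**2. The cut-off convention.** The synopsis exclusion list, section 13.4 and the severity sentence in section 15 all use 30 or above. Only the synopsis trigger uses above 30. On whole-number totals the conventions differ at exactly 30 and nowhere else. This is the smaller point.

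**3. Where participants start.** A total of 30 or above excludes from surgery, so an eligible implanted participant enters at 29 or less. The total would have to rise by at least 31 − 29 = 2 points before the synopsis condition was met. This does not mean that the texts conflict for every participant; the answers must also suggest suicidal thoughts.

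**4. Number of forms, as a scale only.**

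- Table 2 lists the BDI 9 times: once at screening, and at weeks 12, 16, 20, 24, 32, 40, 48 and 52. That is 1 + 8 = 9, which agrees with the table's own count.
- Table 1 and section 14.3.1 also place a BDI at the week-2 baseline. It precedes surgery and does not change the post-implant count.
- Post-implant ceiling in the 52-week study: 12 × 8 = 96 forms, if all 12 complete.
- Extension: 104 / 12 = 8.67, hence 8 complete 12-week intervals per participant who joins and stays. The number joining is not given: 0 joining gives 0 forms, 6 give 6 × 8 = 48, and 12 give 12 × 8 = 96.
- The 8 is nominal. Twelve-week steps from week 52 fall at weeks 64, 76, 88, 100, 112, 124, 136 and 148. The required visits at weeks 104 and 156 are off that grid, and the protocol does not say whether a BDI is given at them.

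These are counts of scheduled questionnaires, not of affected participants. The share of forms that would fall in the second and third rows of the table cannot be derived from the documents, and none is assumed.

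**The case against.** The strongest reply is that the parenthesis was never meant as a condition. The operative words in the synopsis are that the BDI suggests suicidal thoughts. The bracket follows the name of the instrument and may be a loose echo of the severity sentence in section 15. Harm would require staff to work from a synopsis paragraph on secondary outcomes instead of the Safety section, and to read the bracket as a reason to withhold the scale. There are also other safeguards: 52 adverse-event assessments and 40 telephone interviews in Table 2, the open question at visits and the rule for doubtful events in Appendix 1, unscheduled visits (section 14.3.5), and 24-hour access to staff (section 10.1).

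Much of this stands, and it is why the point is minor. It does not rescue the wording. Read as a condition, the bracket narrows the rule in section 15. Read as a gloss, it misstates the protocol's own cut-off. None of the other safeguards names the Columbia scale.

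It is also fair to say that the cut-off of 30 or above defines severe depression and exclusion, not the Columbia trigger, so that mismatch is one of convention only. No text in the protocol declares section 15 to be the governing version. Preferring it rests on clinical sense: suicidal thoughts should prompt assessment whatever the total score.

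**Conclusion.** The concern holds. One of the only two statements of this safety trigger is wrong as written. Read literally, it would leave out a participant whose BDI suggests suicidal thoughts with a total of 30 or less.

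The correction is minor but should be made. It concerns at most 12 participants and at most 96 post-implant forms in the 52-week study, plus nominally up to 96 in the extension if all 12 join and stay. The texts conflict only on the unknown subset of those forms described above. No endpoint, sample size or planned analysis is affected.

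The conclusion assumes whole-number BDI totals, eligibility applied as written, and a literal reading of the parenthesis. If the bracket is only a gloss, what remains is the inconsistent cut-off at a total of exactly 30.

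**What to change.** Delete the parenthesis (>30) from the synopsis sentence. It then matches section 15 word for word, and the Columbia scale applies at any total when the BDI suggests suicidal thoughts. Changing it to 30 or above would repair the convention but keep the score condition, so deletion is better.

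Two optional additions would help, though neither is needed to remove the contradiction:

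- A cross-reference to the rule in section 12.6.1, so that it plainly covers extension BDIs, including those taken by telephone.
- A line in the CRF completion instructions stating which BDI response counts as suggesting suicidal thoughts, since neither section says. Section 19.1 has those instructions reviewed before enrolment. Sections 12.6.1 and 14.4 suggest treatment has already begun, so this may have to go in as a minor CRF change under section 21.4.

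The cost is one deletion at the next amendment, perhaps a few extra Columbia assessments among 12 people, and no new scheduled assessment.
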